#### Qualitative Data Collection

Key informant interviews (n≤30) and focus group discussions (n≤5) will be conducted by the RC and two RAs (different from the RAs involved in quantitative data collection), who will receive training in qualitative data collection. Participants for qualitative data collection will be purposively selected from the main study sample to represent variation in participants, based on variation in attendance and engagement levels, as well as sociodemographic factors. Attendance lists and BeThere facilitators will be consulted in the process of identifying suitable participants. Additionally, waitlist control group participants will be interviewed during data collection periods (baseline, midline, endline, and three-month follow-up) to determine what psychosocial support services—if any—they may have utilized during the study period. The topic guides that will be used for the semi-structured key informant interviews and focus group will be developed prior to the interviews and data collection.

#### Childcare during BeThere sessions

Childcare will be provided on-site for up to two children per participant. Trained and experienced animators (childcare providers) trained by War Child in childcare and child safety will care for children, with two animators available during each session. The childcare sessions are not structured, and no formal activities are facilitated, to avoid providing any index children attending the childcare with a substantive psychosocial experience that might

confound the results of the study. Various play materials and snacks will be provided, and the childcare workers will ensure the safety and comfort of all children.

#### Compensation for participation/defraying costs of participation

As the assessments and intervention sessions will take place in the communities where participants live, within walking distance from their homes, no transportation costs will be reimbursed. However, refreshments will be provided at both intervention and assessment sessions. This compensation is considered minimal and in line with regular War Child implementation programming and was chosen to avoid difficulties of jealousy within the community amongst non-eligible families, and potential coercion of families to participate in sessions and assessments.

#### Cost-Effectiveness Evaluation

The implementation costs of BeThere will be measured using expenditure records, staff time tracking and ingredients-based costing as necessary. Included will be start-up costs as appropriate (e.g. adapting materials, translation, training facilitators, supervisors, and master trainers, etc.), annualized over several years, and recurrent costs. Only "real life" implementation and coordination costs will be included, i.e. costs related to the research such as randomization or trial-related administration will be excluded. For the present research, the cost-effectiveness evaluation will assess costs for the 9 sessions, on average per participant. We will estimate the cost-effectiveness of each arm as a cost per unit change in the caregiver wellbeing and/or child wellbeing by dividing total costs by total score change. We will assess affordability in the greater context of humanitarian assistance by estimating cost per participant and comparing with humanitarian funding globally. Additional sensitivity analyses on the above results may be performed depending on trends observed in the data.

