#### Trial design

#### Design

This study is a two-armed, parallel group randomized controlled trial, with an intent to treat design, a 1:1 allocation ratio, and a waitlist control comparison condition. The study will involve Dinka-speaking primary caregivers of children aged 3–14 and a subsample of their children aged 7–14 in five communities in Bor County, Jonglei State, South Sudan: Pariak, Ghoi, Taragok, Tibek, and Lenguet. Random allocation to intervention and control arms will be done at the family level to ensure caregivers from the same family do not participate in different arms of the study.

We will evaluate the effectiveness of BeThere—a nine-week preventative group psychosocial support intervention for primary caregivers of children aged 3-14-by measuring multiple parenting and psychosocial outcomes among participating caregivers compared to a waitlist control group of caregivers not participating in a parenting intervention. Quantitative data collection will be done by trained research assistants (RAs) using electronic tablets at four timepoints: baseline, midline, endline, and three-month follow up. Prior to the start of data collection, all research instruments will go through a process of translation, adaptation, cognitive interviewing, and pilot testing. The primary outcome of the study will be an overall score on parenting. Secondary outcomes will be child wellbeing (caregiver- and childreported), caregiver stress, distress, and wellbeing, as well as harsh parenting and parental warmth and responsiveness. Additionally, demographics data will be collected from caregivers and children. We will also record participant attendance to intervention sessions, along with facilitator competence to deliver the intervention and their fidelity in delivering the intervention as planned. Additional qualitative data will be gathered via focus group discussions and key informant interviews. The study will be conducted between January and July 2025.

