#### **Exclusion** criteria

- Under 18 years of age
- Participation by either caregiver in a parenting or stress management intervention in the past six months
- Family does not have a child aged 3–14 years

- Anyone who is unable, even with assistance, to complete the assessment questionnaires
- Unwillingness of either caregiver to give informed consent
- Not fluent in Dinka

Based on the successful implementation of the design in the pilot RCT and RCT in Lebanon, a waitlist control will serve as the comparison group in this study. Participants in the waitlist control group will be given the opportunity to participate in the intervention after the 3-month follow-up assessment has been completed.

This study will involve a waitlist control group for two key reasons:

- 1) While the risk of a nocebo effect among research participants randomized into the control group in waitlist-controlled psychological treatment trials has been raised (Furukawa et al., 2014; Gold et al., 2017; Steinert et al., 2017), there is currently little evidence to show that this is the case for preventative interventions (Gold et al., 2017; Miller, et al., 2023).
- 2) The BeThere intervention has already been shown to be effective among caregivers in Lebanon. Considering the vulnerability of the target population and the lack of existing mental health and psychosocial support services, we do not want to deny control group participants access to the intervention.

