#### Control condition

We will employ a waitlist control condition for this study. Same as the intervention arm, participating caregivers should not take part in a parenting intervention in the six months prior to the start of or during the main study period, including the three-month follow up. Existing mental health and psychosocial support services will remain in place and be available to participants in the control and intervention arms. We will explore what kind of services the control group may have used during the study period through key informant interviews. In addition, a checklist of updates of ongoing mental health and psychosocial support activities and services in the community will be collected monthly by the Research Coordinator.

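### The cost-effectiveness ratio is defined separately for each arm, so it does not use the randomised comparison

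*Protocol*

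**What the plan says.** The Cost-Effectiveness Evaluation section of the Protocol fixes both the quantity and the formula: "We will estimate the cost-effectiveness of each arm as a cost per unit change in the caregiver wellbeing and/or child wellbeing", calculated "by dividing total costs by total score change". It mentions no difference in cost between arms, no difference in effect between arms, and no link to the treatment effect estimated under Analyses. It names no time point.

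On costs, the section says "The implementation costs of BeThere will be measured using expenditure records, staff time tracking and ingredients-based costing as necessary". It limits the scope in that "the cost-effectiveness evaluation will assess costs for the 9 sessions, on average per participant", and adds that "costs related to the research such as randomization or trial-related administration will be excluded".

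The Design section describes "a 1:1 allocation ratio, and a waitlist control comparison condition". The text following the exclusion criteria says when the comparator receives the programme: "Participants in the waitlist control group will be given the opportunity to participate in the intervention after the 3-month follow-up assessment has been completed". Under Control condition, "Existing mental health and psychosocial support services will remain in place and be available to participants in the control and intervention arms"; the costing text does not include those services.

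Tertiary objective 5 presents the economic evaluation as support for taking BeThere to scale. It lists start-up costs, affordability, and cost per group, per person and per improvement. It does not mention an incremental comparison either.

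**The concern.** A ratio that belongs to each arm can only use that arm's own change from baseline. In the BeThere arm, that change mixes the effect of the programme with whatever would have happened anyway, for example secular change or the effect of repeated testing. The waitlist arm is there to remove that second component, and the stated formula leaves it out.

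The matter has practical weight because the figure is meant to inform scale-up. According to Research to date, the previous randomised trial found no significant between-group difference in caregiver wellbeing, and its child wellbeing benefit was not sustained at three months. Those are the two outcomes named as denominators here. If that pattern recurred, a before-after ratio could still give a finite cost per point where the randomised comparison shows little or no effect. The and/or wording, with no time point, also leaves the choice of denominator open until results are known.

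**Working it through.** The Protocol gives no numerical cost-effectiveness figure, so there is none to reproduce. The check is algebraic, with an illustration.

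**Inputs from the Protocol**
- Ratio: one per arm, total costs over total score change (Cost-Effectiveness Evaluation).
- Costs: BeThere implementation for the nine sessions, research costs excluded (same section).
- Waitlist access to BeThere: after the last outcome assessment (text following the exclusion criteria).
- Caregivers per arm: 480 (Randomization).

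**Inputs assumed for illustration (not in the documents)**
- Cost per BeThere participant C = 100 in arbitrary currency; waitlist cost 0.
- BeThere mean change dT = +4, with positive meaning improvement; waitlist mean change dC from −1 to +3.

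**Formulas**
- Stated ratio for BeThere: (C × n)/(dT × n) = C/dT.
- Incremental ratio: (C − 0)/(dT − dC).
- Incremental over stated: dT/(dT − dC). C cancels, so this factor does not depend on the assumed cost.

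**Results.** The stated ratio is (100 × 480)/(4 × 480) = 25 per point, whatever the waitlist does.

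| Waitlist change dC | Incremental ratio | Factor dT/(dT − dC) |
|---|---|---|
| −1 | 100/5 = 20 | 4/5 = 0.80 |
| 0 | 100/4 = 25 | 1 |
| +0.5 | 100/3.5 = 28.6 | 1.14 |
| +1 | 100/3 = 33.3 | 1.33 |
| +2 | 100/2 = 50 | 2 |
| +3 | 100/1 = 100 | 4 |

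As dC approaches dT, the incremental ratio grows without limit while the stated ratio stays at 25. If the waitlist also gained 4 points, the trial would show no effect and the formula would still return 25 per point.

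**The waitlist arm's own ratio.** With no nine-session cost before its last assessment, the numerator is zero. The ratio is then 0 for any improvement, 0/0 for no change, and zero over a negative number for a worsening. The Facilitators section counts 40 groups in each arm, so the waitlist will incur delivery costs later. Using those costs would divide money spent after follow-up by changes measured before it was spent.

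**The case against.** The strongest reply is that this is a loosely worded paragraph about a tertiary objective. Both arms' outcomes are collected, so an incremental ratio can be computed later without any change to design or data, and an analysis plan not shown here may specify it. Most of objective 5 (start-up costs, cost per group, cost per person, affordability) does not use the ratio. All of this stands as a limit on importance. It does not remove the point, because the Protocol does not leave the formula open: it states one, and that formula assigns the ratio to each arm.

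A reader might infer that the formula necessarily flatters BeThere, or that it will make the waitlist look like the most cost-effective option. The documents support neither claim:
- They give no waitlist trend. The Study setting section describes persisting conflict and insecurity, so deterioration is possible, and the bias would then reverse.
- Participants are not selected on a symptom score, so regression to the mean from selection is not an obvious source of waitlist improvement.
- No ranking of arms is planned.
- Zero waitlist cost is an inference from the costing scope and the timing of access; the Protocol does not state it.

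It is also tempting to ask for the parenting total as the leading effect measure. That would be a preference: the Protocol chose caregiver and child wellbeing, which is consistent with objective 5. The choice of interval method can reasonably be left to the analysis plan.

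**Conclusion.** The formula as written is wrong for a two-arm randomised trial. It gives a before-after ratio for each arm and discards the comparison that the trial is designed to provide. The BeThere ratio differs from the cost per point gained by the factor dT/(dT − dC). It understates that cost if the waitlist improves, overstates it if the waitlist worsens, and is unbiased only if waitlist change is zero. In the illustration the factor runs from 0.80 to 4. Those values rest on assumed score changes; the algebra does not. The factor takes waitlist cost as zero within the outcome window and BeThere change as positive and larger than waitlist change.

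The waitlist ratio carries no useful information on any reading of its costs. The correction should be made, but its reach is limited to tertiary objective 5. The primary and secondary efficacy conclusions are untouched.

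**What to change.** In the Cost-Effectiveness Evaluation section, replace the per-arm ratio with an incremental one. The numerator is the difference between arms in mean cost per participant. The denominator is the adjusted intention-to-treat difference between arms in the outcome at a time point named in advance. Add an interval that allows for clustering.

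Report the ratio for both caregiver wellbeing and child wellbeing, in place of the and/or wording. Keep cost per participant as a separate affordability figure.

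This takes about two sentences and uses data already planned. The resulting cost per point may be more or less favourable than the stated formula would give. If the between-arm difference is near zero, the ratio will be unstable and its interval very wide, which correctly reflects what the trial shows.

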#### Research to date

A pilot randomized controlled trial (RCT) was conducted among Syrian refugees in Lebanon in 2017–2019 to test the feasibility of the study methodology and to prepare and plan for a full-size RCT (Miller, et al., 2020). Results from the pilot RCT demonstrated that the proposed study measures and methodology were appropriate for evaluating the effectiveness of the intervention. In the pilot study, BeThere also had a significant, positive impact on parenting, caregiver mental health and psychosocial wellbeing, and child wellbeing, suggesting that it is a promising group intervention for improving parenting in low-resource settings.

Based on the experiences and findings from the pilot study, a fully-powered RCT was conducted in Lebanon among Syrian refugee caregivers in 2019–2020 to evaluate the effectiveness of BeThere (Miller, et al., 2023). However, the study was interrupted by strict COVID-19 lockdowns, a severe economic crisis, and widespread social unrest, which meant that implementation was sub-optimal as not all participants were able to receive the full intervention dosage, influencing trial outcomes.

Regardless of these challenges, the RCT showed that, compared to the control condition, caregivers participating in BeThere had slightly better parenting outcomes, with a reduction in harsh parenting, and a significantly greater decrease in distress. There were no significant between-group differences in caregiver wellbeing or parental warmth and responsiveness. Meanwhile, BeThere was shown to be effective in improving child wellbeing at endline, although this was not sustained at three-month follow up and was only measured as a caregiver-reported outcome instead of child-reported (Jordans et al., 2023). Positive outcomes were more pronounced among the group that received the full nine-session intervention, as opposed to those who received a lower dosage of sessions. The effects observed in the RCT are expected to be under-estimations due to the sub-optimal implementation of the intervention caused by the aforementioned environmental factors.

Furthermore, the findings from the pilot RCT showed stronger effects on participants than those found in the RCT, further suggesting these results are an under-estimation. Thus, the effectiveness of the intervention has not yet been conclusively demonstrated.

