#### Primary outcome measures

#### **Parenting**

Parenting will be assessed using a 24-item parenting scale developed to assess change in parenting in the development and testing of BeThere (Miller et al., 2024). In addition to yielding a total score, the measure includes subscales assessing parental warmth and sensitivity (16 items) and harsh parenting (five items). Internal consistency for the full measure ( $\alpha$  = 0.83) and the parental warmth ( $\alpha$  =0.86) subscale was good in the previous RCT, and was acceptable for the harsh parenting subscale ( $\alpha$  = 0.76). The measure was designed as a parent-reported measure, but for this study we will also develop a child-reported version to give us data on parenting from both caregivers and children. The overall parenting score will be considered a primary outcome, while the two subscales will be secondary outcomes.

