#### **Analyses**

The statistical analyses will be carried out by the trial statistician, who will remain masked to the group randomization until the main analyses are complete. The analyses outlined in this strategy will be primarily based on an intention to treat; a per protocol analysis will be the secondary analysis. The per protocol analysis will include participants who complete the intervention, with completion defined as attending at least seven of the nine sessions, and will exclude any participant who attended fewer than seven sessions. We have powered the study (see the "Sample size" section) as a superiority study at 10 weeks. The first stage of analyses will be a descriptive model of the data to assess completeness of data and the integrity of the data collection system. Participants and area characteristics and demographics will be summarized at baseline. Clinical characteristics that have been measured repeatedly will be summarized at baseline and at the post-randomization follow-up assessments. In addition, patterns of missing data will be described.

The primary outcomes (total score of parenting scale and proxy-reported child psychosocial wellbeing) will be analyzed using linear mixed models to model the mean difference in the total score of parenting scale 10 weeks post-randomization. The linear mixed models will be adjusted for baseline total scores and stratification. A two-level hierarchical model will be employed to improve power and take into account clustering of the parents at the family level. These models utilize maximum likelihood estimation and thus allow for missing outcome data under the missing at random assumption. Associations between post-randomization variables and missingness will be dealt with by multiple imputation, again

under the missing at random assumption. Departures from this assumption will be assessed with a sensitivity analysis. Secondary outcomes, including parental warmth and responsiveness, harsh parenting, caregiver psychosocial wellbeing, stress, and distress, and self-reported child psychosocial wellbeing will be assessed with a similar methodology used for the primary outcomes, using generalized linear mixed models depending on the type of outcome (normal, ordinal).

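### The cost-effectiveness measure lets either wellbeing outcome be dropped and is formed within each arm, when it should be incremental between arms with its uncertainty shown

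*Protocol*

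**What the plan says.** The Cost-Effectiveness Evaluation section of the protocol counts the implementation costs of BeThere and excludes research costs. The formula it gives is "cost per unit change in the caregiver wellbeing and/or child wellbeing by dividing total costs by total score change". It applies that formula to the arms separately: "We will estimate the cost-effectiveness of each arm". It does not say which outcome leads, whether child wellbeing is reported by the caregiver or the child (both are collected), or whether change is taken to endline or to the three-month follow-up. It adds: "Additional sensitivity analyses on the above results may be performed depending on trends observed in the data".

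The Objectives section places cost-effectiveness among the tertiary objectives and names no outcome for it.

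On the previous RCT, the section Research to date reports: "There were no significant between-group differences in caregiver wellbeing or parental warmth and responsiveness". For child wellbeing it reports: "BeThere was shown to be effective in improving child wellbeing at endline, although this was not sustained at three-month follow up".

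**The concern.** There are two faults, and both lie in what the text states.

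First, and/or permits three analyses: caregiver wellbeing, child wellbeing, or both. With reporter and time point open as well, the choice is wider still. Nothing in the protocol prevents the less favourable denominator from being left out after the results are seen.

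Second, a quotient formed inside one arm is not the cost of an effect. The trial has a waitlist arm so that change occurring without BeThere can be subtracted, and the stated formula does not subtract it. For the waitlist arm the formula has almost no meaning: only BeThere implementation is costed, and that arm is offered BeThere only after the three-month follow-up.

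Moving to a between-arm ratio is necessary but not sufficient. Cost divided by an effect near zero has no stable size or sign, and on the protocol's own account a small effect on caregiver wellbeing is possible. At stake is whether the cost per point can be interpreted.

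**Working it through.** The protocol gives no cost, score change or ratio for this evaluation, so there is no figure to reproduce. The within-arm fault follows from algebra. The size of the instability rests on assumed inputs.

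**Within-arm quotient.** Let C be the cost per BeThere participant, b the mean change in the waitlist arm and d the added effect of BeThere.
- BeThere arm, as written: C / (b + d).
- Incremental: C / d, with the waitlist cost taken as zero before follow-up.
- The first divided by the second: d / (b + d).
- For b = 0, 0.5d and d this is 1, 0.67 and 0.50. If the waitlist arm worsens by 0.5d it is 2, so the error can run either way.
- Waitlist arm, as written: 0 / b.

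**Between-arm ratio, caregiver-reported outcome.** From the protocol: 480 caregivers per arm (Randomization) and 10% attrition (Power and sample size), so 480 × 0.9 = 432. Assumed: family design effect 1.15, baseline-to-endline correlation 0.5, cost treated as known.
- SE = √(2/432) × √1.15 × √(1 − 0.25) = 0.063 SD.
- With a known cost, the Fieller 95% interval of the ratio is unbounded exactly when the 95% interval of the effect includes zero. The estimated ratio is negative with probability Φ(−d/SE).

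| True effect (SD) | Interval unbounded | Ratio negative |
|---|---|---|
| 0 | 95% | 50% |
| 0.05 | 88% | 21% |
| 0.10 | 65% | 6% |
| 0.15 | 34% | 1% |
| 0.20 | about 11% | below 1% |

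**Other assumptions.** Without baseline adjustment, from 480 per arm with design effect 1.0 to 432 per arm with design effect 1.5, the 95% half-width is 0.127 to 0.163 SD. The unbounded share is 95% at zero effect, 66–78% at 0.10 SD and 13–33% at 0.20 SD.

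**Reporter.** The child-reported outcome has about 400 children, so 200 per arm, or 180 after 10% attrition. With one index child per family and the same assumed correlation, SE = √(2/180) × √0.75 = 0.091 SD. The choice of reporter therefore changes the precision materially.

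**Effect of and/or.** If neither outcome truly changes, the chance that at least one estimate is positive is 1 − [1/4 + arcsin(ρ)/(2π)]. This is 75% for ρ = 0 and 67% for ρ = 0.5, against 50% for one outcome named in advance. Taking the larger of the two estimates inflates it on average by √((1 − ρ)/π) SE: 0.56 SE at ρ = 0 and 0.31 SE at ρ = 0.7, or about 0.036 and 0.020 SD with the SE above.

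**The case against.** **An analysis plan may settle it.** The lead outcome and the handling of uncertainty are often left to a statistical or economic analysis plan, and none is shown. That is fair for the bootstrap. It does not cover the and/or or the per-arm division, which the protocol itself states.

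**Selective reporting is not planned.** A reader might infer that the denominator will be picked after unmasking. No sentence says so. And/or also allows both outcomes to be reported, and the data-dependent sensitivity analyses add to the main ratio without choosing its denominator. What stands is that the wording leaves the choice open.

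**Wellbeing is a legitimate effect unit.** A reader might infer that the ratio should use the primary outcome and does not. The documents do not support this firmly. The Design section says "The primary outcome of the study will be an overall score on parenting", and the Parenting section agrees: "The overall parenting score will be considered a primary outcome, while the two subscales will be secondary outcomes". But the Analyses section has "The primary outcomes (total score of parenting scale and proxy-reported child psychosocial wellbeing) will be analyzed using linear mixed models", so one permitted denominator is primary on that text. Child wellbeing is also the stated downstream aim, and nothing obliges a tertiary economic objective to use the primary outcome.

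**The previous trial did not find these outcomes unchanged.** Absence of a significant difference is not absence of change, and it concerns caregiver wellbeing only; child wellbeing did improve at endline. The protocol also regards the earlier effects as under-estimates. The sentence on caregiver wellbeing covers parental warmth as well, which supplies 16 of the 24 parenting items, so the parenting total is not shown to be a safer denominator.

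**The stakes are limited.** A reader might infer that the scale-up decision would rest on this ratio. Start-up cost, cost per group, cost per participant and the affordability comparison are also planned, and none depends on the denominator.

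**Suppressing unstable ratios is no remedy.** Printing a ratio only when the effect interval excludes zero would itself select favourable results.

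**Conclusion.** The point holds as a defect in the stated method, at low severity. The and/or leaves the reported outcome open, and the per-arm quotient measures something other than the cost of BeThere's effect; both follow from the text alone. The size of the second fault depends on the unknown waitlist change: a waitlist gain equal to the added effect halves the apparent cost per point.

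The instability figures apply only if the ratio is re-formed between arms, which the protocol does not currently do. They rest on the assumed design effect, correlation and true effects. Within the ranges shown, an unbounded interval is more likely than not at 0.10 SD or below and occurs in about 11–33% of trials at 0.20 SD. They support showing cost and effect jointly. They do not show that either wellbeing outcome is the wrong choice.

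**What to change.** In the Cost-Effectiveness Evaluation section:
- Delete and/or. Report caregiver wellbeing and child wellbeing in every case, stating the reporter and time point of each.
- Replace the per-arm quotient with the between-arm incremental cost and incremental effect, set side by side.
- Show their joint uncertainty with a bootstrap that resamples families, the unit of randomisation, as a cost-effectiveness plane or as net benefit over a range of values per point.
- Do this for every named outcome, whether or not its effect is significant.

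Adding the parenting total as a further effect measure is optional. Before that, reconcile the Design, Parenting and Analyses sections on which outcomes are primary.

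The cost is a few sentences and slightly more analysis of data already planned. The reported cost per point may look less favourable than under the present formula.
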